3.6.1.6 Stanford Sleepiness Scale

Somnolence is a possible side effect of AUSTEDO use. The Stanford Sleepiness Scale will be administered during all scheduled study Visits, including the early termination Visit, if such a Visit happens. Should this side effect develop, it will be at the discretion of the investigator whether to continue AUSTEDO at the current dose, discontinue the study drug, or to reduce the dose to a new, maximum, well-tolerated dose. Figure 5 shown below shows this Scale embedded in a data capture form:

Date: DD – MMM – YYYY Study subject number: _____

Visit Number (circle one): 1 2 3 4 5 Early termination Visit

The AUDYT Trial Stanford Sleepiness Scale

Stanford Sleepiness Scale

Using the 7-point scale below pick what best represents how you are feeling and note the corresponding number on the chart below.

Degree of Sleepiness	Scale Rating
Feeling active, vital, alert, or wide awake	1
Functioning at high levels, but not fully alert	2
Awake, but relaxed; responsive but not fully alert	3
Somewhat foggy, let down	4
Foggy; losing interest in remaining awake; slowed down	5
Sleepy, woozy, fighting sleep; prefer to lie down	6
No longer fighting sleep, sleep onset soon; having dream-like thoughts	7
Asleep	X

3.6.1.7 Mini Mental State Examination

To assess the impact AUSTEDO may have on cognitive function, if any, the Mini Mental State Examination (MMSE)¹⁹ will be administered during Visits 1, 4 and during the early termination Visit, if such a Visit happens. It will remain at the investigator's discretion to either discontinue the study drug, or to reduce the dose to a new, maximum, well-tolerated dose if clinically-significant, new-onset cognitive impairment is identified at any point during the course of the trial, even if detected during Visits during which the MMSE is not administered. Figure 6 shown below shows this Scale embedded in a data capture form:

Date: DD – MMM – YYYY Study subject number: ____

Visit Number (circle one): 1 4 Early termination Visit

The AUDYT Trial Mini Mental Status Examination

Maximum Score	Patient's Score	Questions	
5		"What is the year? Season? Date? Day of the week? Month?"	
5		"Where are we now: State? County? Town/city? Hospital? Floor?"	
3		The examiner names three unrelated objects clearly and slowly, then asks the patient to name all three of them. The patient's response is used for scoring. The examiner repeats them until patient learns all of them, if possible. Number of trials:	
5		"I would like you to count backward from 100 by sevens." (93, 86, 79, 72, 65,) Stop after five answers. Alternative: "Spell WORLD backwards." (D-L-R-O-W)	
3		"Earlier I told you the names of three things. Can you tell me what those were?"	
2		Show the patient two simple objects, such as a wristwatch and a pencil, and ask the patient to name them.	
1		"Repeat the phrase: 'No ifs, ands, or buts.'"	
3		"Take the paper in your right hand, fold it in half, and put it on the floor." (The examiner gives the patient a piece of blank paper.)	
1	4	"Please read this and do what it says." (Written instruction is "Close your eyes.")	
1	<	"Make up and write a sentence about anything." (This sentence must contain a noun and a verb.)	
1		"Please copy this picture." (The examiner gives the patient a blank piece of paper and asks him/her to draw the symbol below. All 10 angles must be present and two must intersect.)	
30		TOTAL	

3.6.1.8 MDS-UPDRS (Part III)

To screen for the development of drug-induced parkinsonism, a possible side effect of AUSTEDO use, the MDS-UPDRS (Part III)²⁰ will be administered during Visits 1, 4 and during the early termination Visit, if such a Visit happens. It will remain at the investigator's discretion to either discontinue the study drug, or to reduce the dose to a new, maximum, well-tolerated dose if clinically-significant, new-onset drug-induced parkinsonism is identified at any point during the course of the trial, even if detected during Visits during which the MDS-UPDRS (Part III) is not administered. Figure 7 shown below shows this Scale embedded in a data capture form:

Figure 7

Date: DD – MMM – YYYYY Study subject number: ____

Visit Number (circle one): 1 4 Early termination Visit

The AUDYT Trial MDS-UPDRS (Part III)

3.1	Speech	
3.2	Facial expression	
3.3a	Rigidity- Neck	
3.3b	Rigidity- RUE	
3.3c	Rigidity- LUE	
3.3d	Rigidity- RLE	
3.3e	Rigidity- LLE	
3.4a	Finger tapping- Right hand	
3.4b	Finger tapping- Left hand	
3.5a	Hand movements- Right hand	
3.5b	Hand movements- Left hand	
3.6a	Pronation- supination movements- Right hand	
3.6b	Pronation- supination movements- Left hand	
3.7a	Toe tapping-Right foot	
3.7b	Toe tapping- Left foot	
3.8a	Leg agility- Right leg	
3.8b	Leg agility- Left leg	

3.9	Arising from chair			
3.10	Gait			
3.11	Freezing of gait			
3.12	Postural stability			
3.13	Posture			
3.14	Global spontaneity of movement			
3.15a	Postural tremor- Right hand			
3.15b	Postural tremor– Left hand			
3.16a	Kinetic tremor– Right hand			
3.16b	Kinetic tremor- Left hand			
3.17a	Rest tremor amplitude- RUE			
3.17b	Rest tremor amplitude- LUE			
3.17c	Rest tremor amplitude- RLE			
3.17d	Rest tremor amplitude- LLE			
3.17e	Rest tremor amplitude- Lip/jaw			
3.18	Constancy of rest			
	Were dyskinesias presen	□ No □ Yes		
	Did these movements interfere with ratings?	□ No □ Yes		

3.6.2 Efficacy assessments

3.6.2.1 Video of dystonia examination

As part of the informed consent, all subjects will agree to have their movement disorders examination videotaped. The video recordings, which include sound, will show a subject's entire body and face, in order to view their overall movement. The videos will be de-identified as much as possible and stored in a HIPAA-compliant drive. Staff will do their best to avoid saying subject's name. Only study staff will have access to the videos. The video data will be kept for a minimum of 3 years prior to destruction. The video names will be formatted in a way that the blinded staff remain blinded. The video will not be used

for any commercial, advertising, or promotional purposes. The following protocol will be followed when videotaping:

General instructions

- Remove shoes and socks, roll long pants up to see feet. Remove glasses, if applicable. Remove food or chewing gum from mouth. Pull long hair away from neck in a clip or rubber band.
- Use a tripod. To prevent shadows, avoid strong overhead or back lighting on the subject, more light on face than behind. Video should be taken from straight in front of the participant, except where stated otherwise.
- Avoid recording the participant's name, date of birth, other identifiers, and people other than
 the subject or staff. Subjects will be identified by the number assigned to them during study
 enrollment.

Part I: Participant is seated in a chair without head support. Feet are resting flat on floor and hands are resting flat in lap. Zoom camera in to capture head and shoulders only. Be sure to capture full face.

- 1. At rest, eyes open for 10 seconds
- 2. At rest, eyes closed gently for 10 seconds
- 3. At rest, after opening eyes, for another 10 seconds
- 4. Squeeze eyes closed, 5 times, for 1 second each, then open eyes and observe for 10 seconds
- 5. Ask participant to repeat each sentence or sound below, one at a time:
 - a. "We mow our lawn all year"
 - b. "We eat eggs every day"
 - c. "He had half a head of hair"
 - d. "The puppy bit the tape"
 - e. "TaTaTa"
 - f. "GaGaGa"
 - g. "PaPaPa"
- 6. Ask the participant to hold long vowel sounds: a. "AHHHHHHH" (5 seconds); b. "EEEEEEE" (5 seconds)
- 7. Stick tongue out as far as possible and hold for 5 seconds
- 8. Open and close mouth as wide as possible 2 times
- 9. Ask: "do you have trouble swallowing?" If yes, ask: "occasional or frequent?"
- 10. Ask: "do you choke?" If yes, ask: "occasional or frequent?"

Part II: Participant is seated in a chair without head support. Feet are resting flat on floor and hands are resting flat in lap. Zoom camera out to capture upper body, including head and both upper limbs.

- 11. Front view, at rest, eyes closed: instruct participant to let head drift to its most comfortable (dystonic) position, 10 secs
- 12. Front view, at rest, eyes open: instruct participant to keep head straight at midline for 1 minute. Assist verbally if necessary for initial placement. Do not ask participant to reposition if the head drifts.
- 13. Front view, with maximum range of motion, instruct participant to:
 - a. Turn head to right, then left, both as far as possible, hold each position for 5 secs
 - b. Tilt ear to right shoulder, then left shoulder, both as far as possible, hold each position for 5 secs
 - c. Look up and extend neck, then look down and flex neck, both as much as possible, hold each position 5 secs

- 14. Roll sleeves up for both arms, use a stable writing table, do not allow any tricks or compensations, non-active hand should rest on table without holding paper, viewing video from the front of the participant (participant may put glasses on at this point):
 - a. Write "TODAY IS A NICE DAY" 3 times with dominant hand on associated recording form
 - b. Write "TODAY IS A NICE DAY" 3 times with non-dominant hand on associated recording form
 - c. Draw spiral with right hand, then with left hand, on recording form (active hand should not rest on table)
 - d. Hold tip of pen over dot with right hand for 10 secs, as close as possible. Do not let pen or hand touch surface
 - e. Hold tip of pen over dot with left hand for 10 secs, as close as possible. Do not let pen or hand touch surface
 - f. Hold up written page for video
- 15. Extend arms/hands supinated towards camera for 5 secs
- 16. Extend arms/hands pronated towards camera for 5 secs
- 17. Flex elbows and hold hands/arms steady without touching in front of chest, 5 secs eyes open
- 18. Finger-to-nose test, slow enough to capture accuracy, 5 trials for each hand

Part III: Participant stays seated. Zoom camera out further to capture entire body, including head and all limbs

- 19. Finger tapping (thumb and forefinger) 10 times for each hand, as big and fast as possible
- 20. Open and close both hands all the way, simultaneously and rapidly, 5 times
- 21. Tap heel on floor then toe on floor in rapid alternations, 5 repeated pairs each side

Part IV: Participant stands. Zoom camera out further to capture entire body, including head and all limbs

- 22. Standing frontal view (5 seconds)
- 23. Standing lateral (right) view (5 seconds)
- 24. Standing back view (5 seconds)
- 25. Walking at least 10 steps away from camera (posterior view) and at least 10 steps towards camera (front view)
- 26. Walking on toes at least 10 steps away from camera, and on heels at least 10 steps towards camera
- 27. Walking in toe-heel-tandem, at least 10 steps away from camera and at least 10 steps back towards camera

Part V (perform these only if applicable):

- 28. Ask if there is anything that can be done to reduce the severity of the dystonia (sensory trick), and demonstrate
- 29. If participant has a task specific dystonia not captured in protocol above, such as playing musical instrument or chewing, please video record the dystonic symptoms while participant performs such tasks.
- 30. If participant is in "Blepharospasm Tools" protocol, conduct this task: Participant seated. Zoom camera in to capture all of head and shoulders only: At rest, eyes open, for 2 minutes (blink as natural)

[figure not shown]
Date: DD – MMM – YYYY Study subject number: ____

Visit Number (circle one): 1 4 Early termination Visit

The AUDYT Trial VIDEO PROTOCOL – WORKSHEET

- 1. Write the following sentence three times with your usual writing hand: Today is a nice day.
- 2. Write the following sentence three times with your other hand: Today is a nice day.
- 3. Copy the following spiral with each hand, starting near the dot for each hand and working out.

Left hand Right hand

4

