8.5.2 Publications

The results of this study will be submitted for publication. The primary publication based on this study must be published before any secondary publications are submitted for publication.

- 9. LIST OF TABLES
- 9.1 Table 1: ABBREVIATIONS AND DEFINITIONS
- 9.2 Table 2: Recommended AUSTEDO titration
- 9.3 Table 3: Expected study drug titration for subjects able to increase AUSTEDO to 48 mg/day
- 9.4 Table 4: Expected study drug titration for subjects able to increase AUSTEDO to 36 mg/day
- 9.5 Table 5: Strong CYP2D6 inhibitors
- 9.6 Table 6: Drugs causing QTc prolongation

- 10. LIST OF FIGURES
- 10.1 Figure 1: Adverse Event Documentation Form
- 10.2 Figure 2: Physical Exam Form
- 10.3 Figure 3: Vital signs Form
- 10.4 Figure 4: Columbia Suicide Severity Rating Scale
- 10.5 Figure 5: Stanford Sleepiness Scale
- 10.6 Figure 6: Mini Mental Status Examination
- 10.7 Figure 7: MDS-UPDRS (Part III)
- 10.8 Figure 8: VIDEO PROTOCOL WORKSHEET
- 10.9 Figure 9: Patient Global Impression of Improvement
- 10.10 Figure 10: Clinical Global Impression of Improvement Scale
- 10.11 Figure 11: Global Dystonia Rating Scale

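### The video script has subjects hold up to the camera a worksheet with date and visit-number fields, although raters must be blind to both

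*Combined protocol and SAP*

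**What the plan says.** The synopsis (Design) and sections 2.4 and 3.1 all state that the videos go to raters who do not know the visit number or the recording date. The synopsis adds treatment to that list.

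In Part II of the video script (section 3.6.2.1), item 14 has the subject write a sentence "3 times with dominant hand on associated recording form", repeat it with the other hand, and then "Draw spiral with right hand, then with left hand, on recording form". Item 14f ends the sequence: "Hold up written page for video".

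The worksheet printed after the script appears in the List of Figures (section 10) as "Figure 8: VIDEO PROTOCOL WORKSHEET". Its header has fields for the date and the study subject number, and the line "Visit Number (circle one): 1 4 Early termination Visit".

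Section 3.6.2.1 also gives the protective measures for the footage. "The videos will be de-identified as much as possible", staff are to avoid recording the participant's "name, date of birth, other identifiers, and people other than" the subject or staff, and file names are to be formatted so that blinded staff stay blinded. Section 3.6.2.3 adds that each subject's two videos are randomly labelled A and B, unrelated to the order of recording.

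**The concern.** The two facts that raters must not know are the two that the worksheet header asks staff to record, and the script has that page shown to the camera. If the header is filled in and readable at that moment, the A/B labelling no longer conceals the order.

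The trial has one arm and is open-label, so the CGI-I and GDS, both scored from these videos (section 3.7.2.2), are its only blinded efficacy measures. The CGI-I form asks which of two videos shows the better dystonia. Hidden visit order is what keeps a rater's expectation of improvement out of that answer. The Visit 1 video is made before the drug is started and the Visit 4 video at the end of maintenance, so a visit number also reveals treatment status.

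**Working it through.** The plan gives no figure to reproduce on this point. The check sets the passages side by side.

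**1. Is the recording form the worksheet?** The protocol does not say so outright. The tasks compare as follows:

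| Script, section 3.6.2.1, Part II | Worksheet |
|---|---|
| 14a: sentence three times, dominant hand | Task 1: "Write the following sentence three times with your usual writing hand: Today is a nice day" |
| 14b: sentence three times, non-dominant hand | Task 2: the same sentence three times, other hand |
| 14c: spiral, right hand then left | Task 3: copy a spiral with each hand |
| 14d-e: pen tip held over a dot, each hand | No readable counterpart in the text available |
| 14f: page held up to the camera | Header: date, subject number, visit number |

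All 3 legible worksheet tasks match items 14a to 14c, in the same order. Section 10 lists 11 figures, and 1 of the 11 has these tasks. No other form in the protocol fits the script.

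**2. Does any safeguard reach the header?**

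| Safeguard | What it covers | Names a date or visit number in the picture? |
|---|---|---|
| General de-identification (3.6.2.1) | Who the subject is | No |
| Avoid recording name, birth date and other identifiers (3.6.2.1) | Who the subject is | No |
| Blinded file names (3.6.2.1) | The file name | No |
| Random A/B labels (3.6.2.3) | The label | No |

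Nothing says to leave the header blank, cover it, crop it or mask it.

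**3. How do the raters' own forms compare?** Of the 2 forms that raters complete (CGI-I and GDS), 0 have a visit-number field; both refer to Video A and Video B. Both do carry a date field, which may well be the date of rating. The worksheet header instead follows the pattern of the forms completed at the site, such as the MDS-UPDRS form in section 3.6.1.8.

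**4. How much is exposed at most?**

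- Subjects: 15 (section 3.3). Videos per subject sent to raters: 2, one from Visit 1 and one from Visit 4 (section 3.6.2.3).
- Rated videos: 15 x 2 = 30, or 15 pairs.
- A pair holds exactly one video from each visit, so one readable visit number in either video fixes the order of both. Dates give the order if both are readable.
- Endpoints exposed: 2 secondary efficacy endpoints, the CGI-I and the GDS (section 3.7.2.2). Endpoints not exposed: the tolerability proportion (section 3.7.1.1) and the PGI-I (section 3.7.2.1), neither of which uses the videos.

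The share of pairs actually affected cannot be derived. It depends on when the header is completed, how legible it is and how the page is laid out, none of which is stated.

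**The case against.** The strongest reply is that this is an unstated operational detail and not a contradiction. No sentence tells staff to complete the header before filming, to show it to the camera, or to send unedited footage. A site could satisfy both item 14f and the blinding rule by leaving the header blank until afterwards, showing only the writing, or masking the segment. The instruction about other identifiers is open-ended and could be read to cover visit and date. The page layout is not available, and Part II is framed on the head and both upper limbs, so the header may be unreadable. The exposed endpoints are secondary, in a 15-subject pilot that the protocol says is not powered for efficacy. Without a control arm, even perfectly blinded ratings cannot separate drug effect from natural change.

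Much of this stands. Disclosure is conditional, no rate can be attached to it, and the primary endpoints are untouched. It does not remove the point. Using the worksheet as designed and following the script as written puts the two concealed facts in front of the camera, and the blinding then depends on a precaution that nobody is told to take. The listed identifiers most naturally concern who the subject is, which neither a visit number nor a recording date reveals. Holding the page up also serves little purpose unless its contents can be read, and the header belongs to the same form. Low power limits the weight placed on the CGI-I and GDS, but it does not justify losing the one protection these ratings have against expectation.

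**Conclusion.** The point holds. The worksheet and item 14f are inconsistent with the statement that raters do not know visit number or recording date, and no stated safeguard closes the gap. This is a route to unblinding, not evidence that unblinding occurs.

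All 15 pairs could be exposed at most, with consequences confined to the CGI-I and GDS. These measures serve two of the three secondary objectives, so the inconsistency should be corrected, but it does not threaten the tolerability result or the PGI-I.

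The conclusion assumes that the recording form named in item 14 is the video worksheet, which the matching tasks strongly support but the text never states. Actual loss of blinding would further require the header to be completed before the page is shown and to be legible in the footage.

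**What to change.** - **Worksheet:** move the date and visit-number fields to the side that is not filmed, or state that they are completed only after filming. The subject number can stay, since the raters' own forms already carry it.
- **Item 14f:** specify that only the writing and drawing area is shown, with no date or visit field in view.
- **Existing footage:** before release to raters, have a named member of the study team who is not a rater review this segment and mask any readable date or visit number. The protocol does not describe how staff roles are divided, so this person has to be designated. The check must come before rating, because a rater who has already seen the order cannot be re-blinded.

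The cost is one form revision, one line in the script and a short review of any videos already recorded. Subjects have no extra visits or procedures, and no endpoint changes.

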3.6.2.2 Patient Global Impression of Improvement Scale

During Visit 4, subjects will be asked to assess their dystonic symptoms using the Patient Global Impression of Improvement Scale (PGI-I). Figure 8 shown below shows this Scale embedded in a data capture form:

Date: DD – MMM – YYYY	Study subject number:
Visit Number 4	

The AUDYT Trial Patient Global Impression of Improvement

Please check the one number that best describes how your dystonia is now compared to when you started your participation in the AUDYT trial:

- 1 Very much better
- 2 Much better
- 3 A little better
- 4 No change
- 5 A little worse
- 6 Much worse
- 7 Very much worse

Raters will be provided 2 videos for every study subject: one recorded during Visit 1, and another recorded during Visit 4. Videos will be randomly labeled as Video A and Video B for each subject, but the letter assigned will have no correlation with the order in which the videos were captured. The raters will be asked to make a global comparison of both videos, and to record their assessment using the form shown in Figure 9 below:

Date: DD - MMM - YYYY	Study subject number:

To be filled out by blinded video rater

The AUDYT Trial Clinical Global Impression of Improvement Scale

Please select the option that best describes the change in this subject's dystonia between videos A and B:

1	This subject's dystonia is very much better in Video A compared to Video B
2	This subject's dystonia is much better in Video A compared to Video B
3	This subject's dystonia is a little better in Video A compared to Video B
4	This subject's dystonia is unchanged between Videos A and B
5	This subject's dystonia is a little better in Video B compared to Video A
6	This subject's dystonia is much better in Video B compared to Video A
7	This subject's dystonia is very much better in Video B compared to Video A

Besides performing CGI-I for the videos, raters will be ask to evaluate the severity of the dystonia in each video supplied. The Dystonia Study Group developed the Global Dystonia Rating Scale (GDS) to serve as an instrument to assess dystonia severity. Figure 10 shown below shows the Global Dystonia Rating Scale²¹ embedded in a data capture form:

Figure 11

Date: DD – MMM – YYYY Study subject number: _____

Please circle the video for which this form is used:
Video A Video B

The AUDYT Trial Global Dystonia Rating Scale

BODY REGION SCORED	CLINICAL NOTES (Optional)		ore 10)		
EYES & UPPER FACE					
LOWER FACE (including platysma)					
JAW & TONGUE					
LARYNX (including pharynx)					
NECK					
SHOULDER & PROXIMAL ARM		R	L		
ELBOW, DISTAL ARM, HAND		R	L		
PELVIS & UPPER LEG		R	L		
DISTAL LEG & FOOT		R	L		
TRUNK					
TOTAL SCORE (Sum of all body parts)					

Rate the patient according to body part indicated from 1-10, in relationship to all patients. A score of 0 is no dystonia in that body area. A score of 5 is moderate dystonia. A score of 10 is the most severe dystonia encountered. If the dystonia changes during the examination, rate the maximal dystonia. For mixed motor syndromes, rate only dystonia and not the other components.

- 3.7 Study Endpoints
- 3.7.1 Safety Endpoints
- 3.7.1.1 Primary Safety Endpoint

The primary safety endpoint for the AUDYT trial will be the proportion of study subjects able to titrate up to 48 mg/d (or up to 36 mg/d if receiving a strong CYP2D6 inhibitor) and able to complete the study at this dosage. The reason(s) why subjects are unable to titrate or maintain the maximal recommended AUSTEDO dose will be recorded and reported, when appropriate.

